Study Procedures	Screening			Study Treatment ^d (week/cycle number)																		Follow-up	
	≤ 28 days ^a	≤ 10 days ^b	≤ 72 hour ^c	1	2	3	4	5	6	7	8	9	10	11	12	13	14	15	16	17	18	Safety ^e	Survival ^f
				Cycle 1			Cycle 2			Cycle 3			Cycle 4			Cycle 5			Cycle 6				
CENTRAL LABORATORY TESTS																							
HSV-1 IgG Antibody Serostatus				X						X												X	
Blood and Urine for qPCR ^l				X	X	X	X	X	X	X			X									X	
Swab of Injection Site Surfaces and Occlusive Dressings ^u				X	X	X	X	X	X	X													
Swab of Oral Mucosa ^v				X	X	X	X	X	X	X												X	
Swab of Herpetic Lesion for qPCR ^w				Within 3 days of occurrence of suspected lesion of herpetic origin																			
Radiographic (CT, PET/CT, or MRI) Scans & Tumor Assessment ^x	X												X									X	X
Optional liver ultrasound ^y		X																					
TREATMENT ADMINISTRATION																							
Talimogene Laherparepvec ^z				X			X			X			X			X			X				
Pembrolizumab ^{aa}				X			X			X			X			X			X				
Post-treatment Observation ^h				X			X			X			X			X			X				
REPORTING EXPOSURE TO TALIMOGENE LAHERPAREPVEC																							
Exposure of Subject's Household member or Caregiver ^{ab}				—————→																			
Exposure of Subject's Healthcare Provider ^{ab}				—————→																			

Footnotes and abbreviations after Table 13 below.

Table 13. Part 2 Schedule of Assessments for Talimogene Laherparepvec and Pembrolizumab Combination Treatment: Post Cycle 6

Study Procedures	Study Treatment ^d (week/cycle number)																			Follow-up	
	19	20	21	22	23	24	25	26	27	28	29	30	31	32	33	34	35	36	Pembrolizumab and Talimogene Laherparepvec Cycles 7-35	Safety ^e	Survival ^f
	Cycle 7			Cycle 8			Cycle 9			Cycle 10			Cycle 11			Cycle 12					
GENERAL ASSESSMENTS																					
Informed Consent																					
Review of Eligibility Criteria																					
Demographics																					
Medical and Surgical History																					
Vital Signs ^{g, h}	X			X			X			X			X			X			X	X	
Physical Exam	X																			X	
Weight	X			X			X			X			X			X			X	X	
ECOG Performance Status	X			X			X			X			X			X			X	X	
12-lead ECG																				X	
Child-Pugh Score																				X	
Recording of Concomitant Medication ⁱ	—————→																			X	X ⁱ
Review of DREs, AEs and SAEs ⁱ	—————→																			X	X
Survival Assessment																					X
LOCAL LABORATORY TESTS																					
Chemistry ^k	X			X			X			X			X			X			X	X	
Hematology ^k	X			X			X			X			X			X			X	X	
Coagulation (PT/INR and PTT or aPTT) ^k	X			X			X			X			X			X			X	X	
Thyroid Function Tests (T3, FT3, FT4, TSH) ^j	X						X													X	
Urine or Serum Pregnancy Test ^m																				X	
Serum LDH ^o	X									X										X	
Hepatitis B and C Testing ^p																				X	
CEA (CRC Subjects Only) ^o	X									X										X	
AFP (HCC Subjects Only) ^o	X									X										X	

Footnotes and abbreviations after Table 13 below.

Table 13. Part 2 Schedule of Assessments for Talimogene Laherparepvec and Pembrolizumab Combination Treatment: Post Cycle 6

Study Procedures	Study Treatment ^d (week/cycle number)																		Follow-up		
	19	20	21	22	23	24	25	26	27	28	29	30	31	32	33	34	35	36	Pembrolizumab and Talimogene Laherparepvec Cycles 7-35	Safety ^e	Survival ^f
	Cycle 7			Cycle 8			Cycle 9			Cycle 10			Cycle 11			Cycle 12					
CENTRAL LABORATORY TESTS																					
HSV-1 IgG Antibody Serostatus																				X	
Blood and Urine for qPCR ^l																				X	
Swab of Oral Mucosa ^v																				X	
Swab of Herpetic Lesion for qPCR ^w			Within 3 days of occurrence of suspected lesion of herpetic origin																		
RADIOGRAPHIC TUMOR/RESPONSE ASSESSMENTS																					
Radiographic (CT, PET/CT, or MRI) Scans & Tumor Assessment ^x	X								X										X	X	X
TREATMENT ADMINISTRATION																					
Talimogene Laherparepvec ^z	X			X			X		X			X			X				X		
Pembrolizumab ^{aa}	X			X			X		X			X			X				X		
Post-treatment Observation ^{g,h}	X			X			X		X			X			X				X ^{ac}		
REPORTING EXPOSURE TO TALIMOGENE LAHERPAREPVEC																					
Exposure of Subject's Household member or Caregiver ^{ab}	→																				
Exposure of Subject's Healthcare Provider ^{ab}	→																				

Footnotes on the next page of the table

AE = adverse event; AFP = alpha fetoprotein; aPTT = activated partial thromboplastin time; CEA = carcinoembryonic antigen; CRC = colorectal adenocarcinoma; CRF = case report form; CT = computed tomography; DRE = disease related event; ECG = electrocardiogram; ECOG = Eastern Cooperative Oncology Group; FT3 = free triiodothyronine; FT4 = free thyroxine; HCC = hepatocellular carcinoma; HSV-1 = herpes simplex virus type 1; IgG = immunoglobulin G; INR = international normalization ratio; LDH = lactate dehydrogenase; MRI = magnetic resonance imaging; PET = positron emission tomography; PK = pharmacokinetics; PT = prothrombin time; PTT = partial thromboplastin time; qPCR = real-time polymerase chain reaction; SAE = serious adverse event; T3 = triiodothyronine; TSH = thyroid-stimulating hormone

^a Procedures to be performed \leq 28 days prior to enrollment.

^b Procedures to be performed \leq 10 days prior to enrollment.

^c Procedures to be performed \leq 72 hours prior to enrollment.

^d During treatment, assessments and procedures will be performed within \pm 3 days of the planned visit, unless otherwise specified.

^e Safety follow-up will be performed 30 (+ 7) days after the last dose of talimogene laherparepvec.

^f Subjects will be followed for survival by clinic visit or telephone contact every 12 weeks \pm 28 days from the date of the safety follow-up visit until up to approximately 24 months after the date of last subjects enrolled in Part 2 per tumor type. Subsequent anti-cancer treatments will be collected as part of the long-term follow-up survival assessment.

^g Vital signs (blood pressure, resting heart rate, respiration rate, and temperature) must be performed prior to each talimogene laherparepvec administration.

^h Subjects having intrahepatic injections will undergo a 6 hour observation period after each dose of talimogene laherparepvec with vital signs (temperature, resting heart rate, systolic and diastolic blood pressure and respiratory rate) recorded every 30 minutes for the first 2 hours and hourly for the next 4 hours and once at the end of the observation period. The subjects should be hospitalized if there is clinical deterioration during any observation period. Subjects who have cutaneous, subcutaneous, or nodal injections (no intrahepatic injections) must undergo a 1 hour observation period including vital signs at 30 minutes and 1 hour. **As of Protocol Amendment 6 (dated 26 October 2021), intrahepatic injections of talimogene laherparepvec and liver biopsies are no longer performed in this study.**

ⁱ All serious adverse events follow up to a serious adverse event, including death due to any cause that occur after the subject has signed the main informed consent through 90 (+7) days after the last administration of talimogene laherparepvec or pembrolizumab, or 30 (+7) days following cessation of treatment if the subject initiates new anticancer therapy, whichever is earlier, will be reported to Amgen and recorded in the case report form. In addition, all serious adverse events that occur during the long-term safety follow-up period until the end of study are to be reported to Amgen and recorded in the CRF. As described in Section 9.2.3.2, there is no requirement to monitor study subjects for serious adverse events following the protocol required reporting period (as defined in Section 9.2.3) or after the end of study. However, these serious adverse events should be reported to Amgen (regardless of causality) if the investigator becomes aware of them (per regional regulatory requirements). All serious adverse events must be submitted to Amgen within 24 hours following the investigator's awareness of the event via the applicable CRF. All disease-related events and non-serious adverse events that occur, and concomitant medications that are administered after the first dose of talimogene laherparepvec or pembrolizumab through 30 (+7) days after the last administration of talimogene laherparepvec or pembrolizumab will be recorded in the events CRF.

^j Only subsequent anti-tumor treatment will be recorded.

^k During treatment blood samples for chemistry, hematology and coagulation panels will be collected weekly for the first 7 weeks of treatment and then prior to each talimogene laherparepvec administration until end of study treatment.

^l Blood samples for thyroid function tests (triiodothyronine [T3] or free T3 [FT3] per local standard, free thyroxine [FT4], and thyroid-stimulating hormone [TSH]) will be collected at screening. Samples will be collected prior to study treatment administration on day 1 of weeks 1, 7, 13, 19, 25 and every 12 weeks thereafter until end of pembrolizumab treatment. Blood sample will also be collected at the safety follow-up visit. Note: Thyroid Function Tests must be collected, but if there are no symptoms of hypothyroidism or hyperthyroidism, study treatment can be initiated prior to the reporting of the laboratory results.

- ^m Urine or serum pregnancy test to be performed on female of childbearing potential. Additional on-treatment pregnancy testing may be performed at the investigator's discretion or as defined in a county-specific protocol supplement at the end of the Appendix Section of the protocol as required per local laws and regulations.
- ⁿ Disease specific assessments will only be performed on archived tissue (preferred) or screening biopsy tissue if results from previous testing are not available. Results should be submitted during screening and any time after enrollment. For details and a list of disease specific assessments refer to Section 7.2.1. For CRC subjects, if historical results are not available, the tests have to be completed locally. However, they do not need to be available at the time of enrollment.
- ^o During treatment blood samples for lactate dehydrogenase (LDH), carcinoembryonic antigen (CEA), alpha-fetoprotein (AFP) will be collected at screening and at week 10 (± 1 week) and then every 9 weeks (± 1 week) prior to talimogene laherparepvec administration until end of study treatment.
- ^p If serology was negative and > 1 month ago the hepatitis panel should be repeated during screening. Subjects who are positive for hepatitis B virus (HBV) and hepatitis C virus (HCV) infection should receive additional testing of viral load by polymerase chain reaction (PCR) and HCV genotyping (if applicable) at screening, , and at the safety follow-up. For additional information refer to Section 7.2.1 through 7.2.3.1. In addition, HBSAg testing should be performed if ALT is elevated > 5 x ULN and/or > 3 x baseline in subjects with hepatitis B. Refer to Table 15 for more details.
- ^q Repeated Hepatitis B and/or C testing is only needed for Arm VI (HCC with well-controlled hepatitis).

^l During treatment blood and urine sample for real-time polymerase chain reaction (qPCR) testing of talimogene laherparepvec deoxyribonucleic acid (DNA) will be performed at the following time points: all subjects at weeks 1 and 4 will have samples taken prior to talimogene laherparepvec administration and 7 days (± 2 days) and 14 days (± 2 days) after talimogene laherparepvec administration and for subjects receiving intrahepatic injections additional samples will be taken at 1 hour [± 15 minutes]; following talimogene laherparepvec administration; on Week 7 prior to talimogene laherparepvec administration; on Week 10 prior to talimogene laherparepvec administration; and at safety follow-up visit. **As of Protocol Amendment 6 (dated 26 October 2021), intrahepatic injections of talimogene laherparepvec and liver biopsies are no longer performed in this study.**

^u Swabs of the surface of the injection sites and exterior of occlusive dressings for qPCR testing of talimogene laherparepvec DNA with or without 50% Tissue Culture Infective Dose (TCID50) assay of talimogene laherparepvec virus. During treatment the surface of the injection site will be swabbed at the following timepoints: on Weeks 1 and 4 prior to talimogene laherparepvec administration 7 (± 2) days, and 14 (± 2) days following talimogene laherparepvec administration; on Week 7 prior to talimogene laherparepvec administration. During treatment the exterior surface of the injection site dressings will be swabbed at the following timepoints: 7 (± 2) days after Week 1 and 4 talimogene laherparepvec administrations.

- ^v Swabs of oral mucosa: During treatment swabs of oral mucosa for qPCR testing of talimogene laherparepvec DNA with or without TCID50 assay for talimogene laherparepvec virus will be collected at the following visits: Week 1 and 4 prior to talimogene laherparepvec administration and 7 (\pm 2) days and 14 (\pm 2) days following talimogene laherparepvec administration; Week 7 prior to talimogene laherparepvec administration. During safety follow-up, swabs of oral mucosa will be collected at the 30 (+ 7) day safety follow-up visit for qPCR testing of talimogene laherparepvec DNA.
- ^w Swabs of any lesion suspected to be herpetic in origin (if any) will be collected during treatment and safety follow-up as follows: subject should return to clinic within 3 days of the occurrence of reportable lesion suspected to be herpetic in origin such as cold sores or vesicles. The lesion should be evaluated by the investigator and swabbed if HSV infection is suspected. The sample will be sent to the central laboratory for detection of talimogene laherparepvec DNA using qPCR testing.
- ^x Radiographic tumor imaging: During treatment, radiographic tumor imaging will be performed independent of treatment cycle at week 10 (\pm 1 week) and then every 9 weeks (\pm 1 week) until confirmed progressive disease (PD) per modified immune-related response criteria (irRC) simulating RECIST version 1.1 (irRC-RECIST) ([Appendix D](#)). Radiographic imaging is required at the safety follow up visit if the subject ended treatment prior to documentation of confirmed PD per modified irRC-RECIST and has not had radiographic tumor imaging performed within 9 weeks (\pm 1 week) of the visit. Every effort should be made to complete radiographic assessments during the long-term follow-up every 12 weeks (+ 1 week) until documented confirmed PD per modified irRC-RECIST, start of new anticancer treatment, death, or end of study, whichever occurs first, for subjects discontinuing study treatment for any reason other than confirmed PD. Response (complete response [CR], or partial response [PR]) or disease progression to be confirmed by second consecutive radiographic assessments no less than 4 weeks from the date of the first documented response or disease progression. Note: Confirmation of disease progression is required only in the absence of rapid clinical deterioration (ie, rapid decline in performance status) or symptomatic disease requiring rapid initiation of alternative systemic anti-cancer therapy.
- ^y To be performed if required by site for assessment of the intrahepatic lesion injection location. **As of Protocol Amendment 6 (dated 26 October 2021), intrahepatic injections of talimogene laherparepvec and liver biopsies are no longer performed in this study.**
- ^z If no progression is seen after a total of 12 cycles, a total of 35 cycles of talimogene laherparepvec, at maximum tolerated dose if known or otherwise previously received dose, every 21 (\pm 3 days) may be administered, or the subject may proceed to alternative therapies depending on investigator discretion. Dosing with talimogene laherparepvec beyond 12 cycles may be done if in the opinion of the investigator, the subject is deriving clinical benefit.
- ^{aa} Pembrolizumab will be administered intravenously to subjects randomized at a dose of 200 mg every 3 weeks (\pm 3 days) starting at day 1 of week 1 until confirmed PD per modified irRC-RECIST (The same pattern of assessments continue if treatment exceeds week 18). Subjects can receive up to 35 cycles (approximately 24 months) with pembrolizumab.
- ^{ab} Reporting potential or known unintended exposure to talimogene laherparepvec: If a household member, caregiver, or healthcare provider who has had close contact with the subject is suspected to have been exposed to talimogene laherparepvec (eg, has signs or symptoms suspected to be herpetic origin or is accidentally exposed to talimogene laherparepvec), report the potential or known unintended exposure to talimogene laherparepvec, suspected related signs or symptoms, and detection of talimogene laherparepvec DNA by qPCR testing in a swab taken from a lesion, if any, in a subject's household member, caregiver, or healthcare provider.
- ^{ac} Post treatment observation will only be needed after cycle 12 where talimogene laherparepvec is being injected into liver.

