Upon permanent discontinuation from the study treatment for any reason, the following procedures will be performed 30 (+7) days after the last dose of talimogene laherparepvec for the monotherapy cohorts (Cohorts 1, 2, 3 and 4, in Part 1); and will be performed 30 (+ 7) days after the last dose of talimogene laherparepvec or pembrolizumab, whichever is later, for the combination treatment (Cohorts 5 and 6 in Part 1 and all arms in Part 2):

- Vital signs, physical examination including weight, ECOG, and ECG
- Local laboratory assessments: hematology panel, chemistry panel, LDH, coagulation tests, serum or urine pregnancy test for females of childbearing potential, CEA in CRC and GEC adenocarcinoma only, AFP in HCC only, CA 19-9 (Part 1 only) in CRC, GEC, HCC only, HBV DNA by PCR or HCV RNA by PCR for subjects with history of or chronic HBV or HCV infection, respectively
- Child-Pugh score
- Central laboratory assessments: ██████████, HSV-1 IgG antibody serostatus, and qPCR testing for talimogene laherparepvec DNA; urine for qPCR testing of talimogene laherparepvec DNA; swabs of the oral mucosa for qPCR testing of talimogene laherparepvec DNA; swabs of cold sores, vesicles and other lesions suspected to be herpetic in origin (if any) for qPCR testing of talimogene laherparepvec DNA.
- Radiographic and clinical tumor assessment
- Reporting disease related events, adverse events, serious adverse events and documentation of concomitant medications
- Reporting potential or known unintended exposure to talimogene laherparepvec as specified in Section 9.4

Long-term Follow-up Procedures:

All subjects who permanently discontinue study drug for any reason other than withdrawal of full consent will be contacted by clinic visit or telephone to assess survival, talimogene laherparepvec-related adverse events, and initiation of additional anti-tumor treatment. For subjects in the combination treatment cohort, the long-term follow-up starts after the discontinuation of whichever study drug is discontinued last.

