3.5 Estimated Study Duration

3.5.1 Study Duration for Subjects

The subject accrual period is planned to be approximately 58 months.

The estimated average per-subject study duration is approximately 32 months. The duration of the screening period for each subject will be up to 28 days. The duration of treatment will vary for each subject. Subjects can receive a maximum of 12 cycles of

talimogene laherparepvec in Part 1 and 35 cycles in Part 2. Subjects will be treated with talimogene laherparepvec until a CR is achieved, all injectable tumors have disappeared, PD per the modified irRC-RECIST ([Appendix D](#)), confirmed by 2 consecutive scans > 4 weeks apart (Nishino et al, 2014), intolerance of study treatment, a total of 6 cycles (including the initial 10^6 PFU/mL cycle) have been administered and in the investigator's opinion further talimogene laherparepvec is not advisable, the subject has received the maximum allowable cycles of talimogene laherparepvec, or the investigator determines it is in the best interest of the subject to discontinue treatment (eg, rapid clinical deterioration or worsening symptomatic disease requiring alternative systemic anti-cancer therapy), whichever occurs first. Confirmation of disease progression is required only in the absence of rapid clinical deterioration (ie, rapid decline in performance status or requiring other therapy) or worsening symptomatic disease requiring a rapid switch to alternative systemic anti-cancer therapy.

Subjects can receive up to 35 cycles (approximately 24 months) with pembrolizumab. During that time, subjects may continue until PD per the modified irRC-RECIST ([Appendix D](#)), unacceptable toxicity, withdrawal of consent, physician's decision to stop therapy for the subject, or sponsor's decision to terminate the study. Discontinuation of treatment may be considered for subjects who have attained a confirmed CR that have been treated for at least 8 cycles (24 weeks) with pembrolizumab, and had at least 2 cycles of pembrolizumab beyond the date when the initial CR was declared.

Subjects will be followed for safety for approximately 30 (+ 7) days after the last dose of talimogene laherparepvec for the monotherapy cohorts, and after the last dose of talimogene laherparepvec or pembrolizumab, whichever is later, for the combination treatment (Cohort 5 and 6 in Part 1, and all arms in Part 2).

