Dosing should be permanently discontinued if, in the opinion of the investigator, the subject develops clinical evidence of any serious herpes infection (such as HSV hepatitis, encephalitis, or disseminated infection). Systemic anti-herpetic drugs (eg, acyclovir, valacyclovir, or famciclovir) should only be reserved for suspected cases of severe herpetic infection as outlined in the Guidelines for Suspected Serious Herpetic Infections document, but topically administered anti-herpetic drugs may be administered for limited suspected herpetic skin lesions after they are swabbed and tested for talimogene laherparepvec using qPCR.

For Part 1 Group A Cohorts 1-6, Part 1 Group B Cohorts 5 and 6a, and Part 2 Arms I-VI, in subjects with history of HBV and HCV, viral load should be rechecked when ALT or AST are elevated more than twice their baseline value. If reactivation of HBV or HCV is confirmed, discontinuation of talimogene laherparepvec and starting hepatitis antiviral medication should be considered after consultation with the sponsor medical monitor.

For Part 1 Group B Cohort 6b and Part 2 Group B Arm VI subjects with well-controlled viral hepatitis, please see [Table 15](#). Subjects who discontinue talimogene laherparepvec are to continue to return for all other study procedures and

measurements including the 30-day safety follow-up visit (ie, until approximately 30 [+ 7] days after the last dose of study drug) and long term survival follow-up.

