Table 11. Part 1 Schedule of Assessments for Talimogene Laherparepvec and Pembrolizumab Combination Treatment: Post Cycle 6

Study Procedures	Study Treatment ^d (week/cycle number)																		Follow-up		
	19	20	21	22	23	24	25	26	27	28	29	30	31	32	33	34	35	36	Pembrolizumab Cycles 7-35	Safety ^e	Survival ^f
	Cycle 7			Cycle 8			Cycle 9			Cycle 10			Cycle 11			Cycle 12					
GENERAL ASSESSMENTS																					
Informed Consent																					
Review of Eligibility Criteria																					
Demographics																					
Medical and Surgical History																					
Vital Signs ^{g, h}	X			X			X			X			X			X			X	X	
Physical Exam	X																			X	
Weight	X			X			X			X			X			X			X	X	
ECOG Performance Status	X			X			X			X			X			X			X	X	
12-lead ECG																				X	
Child-Pugh Score																				X	
Recording of Concomitant Medication ⁱ	→																		X	X ^j	
Review of DREs, AEs and SAEs ⁱ	→																		X	X	
Survival Assessment																				X	
LOCAL LABORATORY TESTS																					
Chemistry ^k	X			X			X			X			X			X			X	X	
Hematology ^k	X			X			X			X			X			X			X	X	
Coagulation (PT/INR and PTT or aPTT) ^k	X			X			X			X			X			X			X	X	
Thyroid Function Tests (T3, FT3, FT4, TSH) ^l	X						X													X	
Urine or Serum Pregnancy Test ^m																				X	
Serum LDH ^o	X									X										X	
Hepatitis B and C Testing ^p																				X	
CEA (CRC and GEC Adenocarcinoma Subjects Only) ^o	X									X										X	
AFP (HCC Subjects Only) ^o	X									X										X	
CA 19-9 (GEC, CRC, and HCC Only) ^o	X									X										X	

Footnotes and abbreviations after Table 11 below.

Table 11. Part 1 Schedule of Assessments for Talimogene Laherparepvec and Pembrolizumab Combination Treatment: Post Cycle 6

Study Procedures	Study Treatment ^d (week/cycle number)																		Follow-up		
	19	20	21	22	23	24	25	26	27	28	29	30	31	32	33	34	35	36	Pembrolizumab Cycles 7-35	Safety ^e	Survival ^f
	Cycle 7			Cycle 8			Cycle 9			Cycle 10			Cycle 11			Cycle 12					
CENTRAL LABORATORY TESTS																					
HSV-1 IgG Antibody Serostatus																				X	
Blood and Urine for qPCR ^l																				X	
Swab of Oral Mucosa ^v	X			X			X			X			X			X				X	
Swab of Herpetic Lesion for qPCR ^w				Within 3 days of occurrence of suspected lesion of herpetic origin																	
Blood for Anti-Pembrolizumab antibody ^x				X																	
Blood for Pembrolizumab PK ^y				X																	

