RADIOGRAPHIC TUMOR/RESPONSE ASSESSMENTS																					
Radiographic (CT, PET/CT, or MRI) Scans & Tumor Assessment ^z	X									X									X	X	X
TREATMENT ADMINISTRATION																					
Talimogene Laherparepvec ^{ab}	X			X			X			X			X			X ^{ab}					
Pembrolizumab ^{ac}	X			X			X			X			X			X			X		
Post-treatment Observation ^{g,h}	X			X			X			X			X			X					
REPORTING EXPOSURE TO TALIMOGENE LAHERPAREPVEC																					
Exposure of Subject's Household member or Caregiver ^{ad}	→																				
Exposure of Subject's Healthcare Provider ^{ad}	→																				

Footnotes on the next page of the table

AE = adverse event; AFP = alpha fetoprotein; aPTT = activated partial thromboplastin time; CA 19-9 = cancer antigen 19-9; CEA = carcinoembryonic antigen; CRC = colorectal adenocarcinoma; CRF = case report form; CT = computed tomography; DRE = disease related event; ECG = electrocardiogram; ECOG = Eastern Cooperative Oncology Group; FT3 = free triiodothyronine; FT4 = free thyroxine; GEC = gastroesophageal cancer (adenocarcinoma or squamous cell carcinoma); HCC = hepatocellular carcinoma; HSV-1 = herpes simplex virus type 1; IgG = immunoglobulin G; INR = international normalization ratio; LDH = lactate dehydrogenase; MRI = magnetic resonance imaging; PET = positron emission tomography; PK = pharmacokinetics; PT = prothrombin time; PTT = partial thromboplastin time; qPCR = real-time polymerase chain reaction; SAE = serious adverse event; T3 = triiodothyronine; TSH = thyroid-stimulating hormone

^a Procedures to be performed \leq 28 days prior to enrollment.

^b Procedures to be performed \leq 10 days prior to enrollment.

^c Procedures to be performed \leq 72 hours prior to enrollment.

^d During treatment, assessments and procedures will be performed within \pm 3 days of the planned visit, unless otherwise specified.

^e Safety follow-up will be performed approximately 30 (+ 7) days after the last dose of talimogene laherparepvec.

^f Subjects will be followed for survival by clinic visit or telephone contact approximately every 12 weeks \pm 28 days from the date of the safety follow-up visit until up to approximately 24 months after the date of last subjects enrolled in Part 2 per tumor type. Subsequent anti-cancer treatments will be collected as part of the long-term follow-up survival assessment.

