7.2.3 Long-term Follow-up

7.2.3.1 Safety Follow-up

Upon permanent discontinuation from the study treatment for any reason, the following procedures will be performed 30 (+7) days after the last dose of talimogene laherparepvec for the monotherapy cohorts (Cohorts 1, 2, 3 and 4 in Part 1), or 30 (+ 7) days after the last dose of talimogene laherparepvec or pembrolizumab, whichever is later, for the combination treatment (Cohorts 5 and 6 in Part 1, and all arms in Part 2).

- Vital signs (systolic/diastolic blood pressure, resting heart rate, respiratory rate, temperature): Subject must be in a supine position in a rested and calm state for at least 5 minutes before blood pressure assessments are conducted. If the subject is unable to be in the supine position, the subject should be in most recumbent position possible. The position selected for a subject should be the same that is used throughout the study and documented on the vital sign CRF. Record all measurements on the vital signs CRF. The temperature location selected for a subject should be the same that is used throughout the study and documented on the vital signs CRF.
- Physical examination as per standard of care
- Weight in kilogram should be measured without shoes
- ECOG performance status assessment
- 12-lead ECG: The ECG must include the following measurements: heart rate, PR, QRS, QT and QTc intervals. Subject must be in supine position in a rested and calm state for at least 5 minutes before ECG assessment is conducted. If the subject is unable to be in the supine position, the subject should be in most recumbent position as possible. The investigator or designated site physician will review all ECGs. Once signed, the original ECG tracing will be retained with the subject's source documents. At the request of the sponsor, a copy of the original ECG will be made available to Amgen.
- Recording of Concomitant Medications: All concomitant medications that are administered after the subject has signed the main informed consent through 30 (+7) days after the last administration of talimogene laherparepvec will be recorded in the concomitant medications CRF.

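### Footnote e of the combination schedules (Protocol Tables 10-11 and 12-13) times the safety follow-up visit from talimogene laherparepvec alone, against the body text, which uses whichever drug is stopped last

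*Protocol*

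**What the plan says.** Four places in the current protocol text give the anchor for combination subjects, apart from the schedules.

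- Section 7.2.3.1 sets the visit at 30 (+7) days after the last dose of either drug, "whichever is later, for the combination treatment (Cohorts 5 and 6 in Part 1, and all arms in Part 2").
- Section 3.5.1 gives the same rule: "whichever is later, for the combination treatment (Cohort 5 and 6 in Part 1, and all arms in Part 2").
- The synopsis, under Safety Follow-up Procedures, says the same: "whichever is later, for the combination treatment (Cohorts 5 and 6 in Part 1 and all arms in Part 2").
- Section 6.2.1.2 addresses subjects who stop talimogene laherparepvec. They keep returning for the remaining procedures, "including the 30-day safety follow-up visit (ie, until approximately 30 [+ 7] days after the last dose of study drug").

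Footnote e of the two combination schedules differs. For Part 1 (Tables 10-11) it reads: "Safety follow-up will be performed approximately 30 (+ 7) days after the last dose of talimogene laherparepvec". For Part 2 (Tables 12-13) it reads: "Safety follow-up will be performed 30 (+ 7) days after the last dose of talimogene laherparepvec".

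Footnote e of the monotherapy schedule (Tables 8-9) has the same content. It is correct there, because those subjects receive only one drug.

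The column layout supports the body text. Table 11 puts a column headed "Pembrolizumab Cycles 7-35" before the safety visit, and Table 13 puts "Pembrolizumab and Talimogene Laherparepvec Cycles 7-35" in the same position.

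**The concern.** The combination schedules appear to have inherited the monotherapy footnote without adding the second drug. No rule says that the body text overrides the footnotes. The synopsis sends readers to Section 7 and the Schedule of Assessments for the timing of procedures, so a site could reasonably work from the table.

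The two anchors separate whenever pembrolizumab continues alone, which Section 8.3.1 allows.

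- **Part 1.** The caps alone can cause it: 12 cycles of talimogene laherparepvec against 35 of pembrolizumab. Part 1 injections went only into liver tumors, and Amendment 6 ended intrahepatic injection. Any Part 1 combination subject still on treatment could then continue only pembrolizumab.
- **Part 2.** Section 6.2.1.1 foresees talimogene laherparepvec stopping for lack of injectable lesions while pembrolizumab goes on.

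At stake is a single visit. In the combination schedules, ECG and Child-Pugh score appear only at screening and at the safety visit. The visit also carries end-of-treatment laboratory, hepatitis and thyroid tests. The thyroid sample at this visit is called for in the schedules but is not in the Section 7.2.3.1 list, so the schedule is the operative source for it. A visit held on the footnote's date would leave these not done after pembrolizumab ends.

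**Working it through.** No sample size, power or error rate depends on this point. The check is a comparison of text plus calendar arithmetic.

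**Anchor for combination subjects, by place**

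| Place | Visit counted from |
|---|---|
| Synopsis, Safety Follow-up Procedures | later of the two drugs |
| Section 3.5.1 | later of the two drugs |
| Section 6.2.1.2 | last dose of study drug |
| Section 7.2.3.1 | later of the two drugs |
| Tables 10-11, footnote e | talimogene laherparepvec only |
| Tables 12-13, footnote e | talimogene laherparepvec only |

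**Inputs**

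- Visit window: 30 (+7) days, that is 30 to 37 days (all places above that state a window).
- Cycle length: 21 days for both drugs, ±3 days (Sections 6.2.1.1 and 7.2.2).
- Caps: talimogene laherparepvec 12 cycles in Part 1 and 35 in Part 2; pembrolizumab 35 cycles (Section 3.5.1).
- Assumption: both drugs start together and no dose is delayed or missed.

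**Formula.** Let k be the number of pembrolizumab cycles given after the last talimogene laherparepvec cycle. The anchors differ by 21k days. The footnote's visit, relative to the last pembrolizumab dose, falls at (30 to 37) − 21k days. The body text always gives +30 to +37.

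| k | Calculation | Footnote visit relative to last pembrolizumab dose |
|---|---|---|
| 0 | 30 to 37 | +30 to +37 days (no conflict) |
| 1 | 30 − 21 to 37 − 21 | +9 to +16 days |
| 2 | 30 − 42 to 37 − 42 | −12 to −5 days (before the dose) |
| 2, both intervals shortened by 3 days | 30 − 36 to 37 − 36 | −6 to +1 days |

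So on nominal cycles the visit precedes the last pembrolizumab dose from k = 2. With the permitted windows used in full, k = 2 is borderline.

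**Part 1 at both caps.** k = 35 − 12 = 23. The gap is 23 × 21 = 483 days, or 69 weeks. By week number: cycle 12 starts in week 1 + 11 × 3 = 34 and cycle 35 in week 1 + 34 × 3 = 103, and 103 − 34 = 69. The footnote visit falls 483 − 37 = 446 to 483 − 30 = 453 days before the last pembrolizumab dose.

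**Part 2.** Both caps are 35, so k = 0 and the gap is 0 if the drugs stop together. As an assumed case, if talimogene laherparepvec ends after cycle 6 and pembrolizumab runs to 35, k = 29 and the gap is 29 × 21 = 609 days (87 weeks).

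**What does not move**

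- Adverse events are collected to 30 (+7) days after the later drug (Section 9.2.2).
- The serious adverse event window runs from the last dose of either drug (Section 9.2.3).
- The SAP's treatment-emergent window uses the later drug, and its treatment period ends 30 days after the last investigational product, which for combination subjects means both drugs (SAP Section 5).
- Long-term follow-up starts after the drug stopped last (Section 7.2.3.2).
- Chemistry continues before each dose of either drug (Section 7.2), and scheduled thyroid tests run to the end of pembrolizumab (thyroid footnotes).
- The visible SAP safety sections plan no ECG or Child-Pugh analysis.

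**The case against.** The best case for the plan is that the subject at risk is already covered. Section 6.2.1.2 speaks directly to someone who stops talimogene laherparepvec. Section 7.2.3.1 triggers the visit on permanent discontinuation of study treatment and then gives the later-drug rule. The columns of Tables 11 and 13 put cycles up to 35 before the visit. The thyroid footnotes run to the end of pembrolizumab and then add the safety-visit sample. A site would have to overlook all of this. In Part 2, talimogene laherparepvec stopped for reasons other than toxicity may be resumed while pembrolizumab continues, so for those subjects the last dose may not be known until pembrolizumab ends and the footnote often cannot be applied literally.

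Most of that stands, and it is why the severity is the lowest. It shows that the intended rule can be recovered, but the footnotes still state a different one.

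A reader might infer three stronger things that the documents do not support.

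- **Post-pembrolizumab safety data would be lost or the adverse event tables truncated.** The collection and analysis windows listed above do not depend on footnote e.
- **Survival follow-up would start early,** because footnote f counts contacts from the safety visit. Section 7.2.3.2 starts long-term follow-up after the drug stopped last.
- **Late immune-related events would be missed.** Section 6.2.2.2.1 says they can arise months after the last dose. Such events would also fall after a correctly timed 30-day visit; the serious adverse event window and long-term follow-up are there for them.

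**Conclusion.** The point holds as an internal inconsistency of the lowest severity. Footnote e is wrong as written in both combination schedules, and no design decision is in dispute. Taken literally, for a subject who continues pembrolizumab alone, it brings the visit forward by three weeks per extra pembrolizumab cycle. That places it before the last pembrolizumab dose from about two extra cycles, and separates the anchors by as much as 69 weeks in a Part 1 subject who reaches both caps. These figures assume nominal 21-day cycles, a common start and no missed or delayed doses. The 69 weeks is an arithmetic extreme, not an expected delay.

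The documents do not say how many subjects were on pembrolizumab alone. Section 4 states that enrollment has stopped, so only subjects still on treatment are concerned. The objective response analysis, the sample size and every other statistical figure are unchanged.

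**What to change.** In footnote e of Tables 10-11 and of Tables 12-13, count the 30 (+7) days from the last dose of whichever of the two drugs is given later, using the wording of Section 7.2.3.1. Leave footnote e of Tables 8-9 as it is.

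Send a short clarification memo now to sites with active combination subjects, citing Sections 6.2.1.2 and 7.2.3.1. Make the wording change in the next amendment, not in one of its own, because Section 12.1 requires investigator agreement and IRB/IEC approval. Amendment 5 made corrections of the same kind to Tables 12 and 13, so there is precedent.

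The cost is one memo, to at most the roughly 50 planned sites (Section 3.2) and probably fewer, plus two edited footnotes. No analysis or sample size changes. A change to the case report forms seems unlikely, but the forms are not among the documents, so that could not be checked.
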